## PLEURAL EFFUSION

- Document pleural effusion as yes or no
- Note the size (small, medium or large)
- If pleural effusion and no lung is seen in the zone = 0 B lines
- If pleural effusion and lung is seen = count number of B lines seen in lung

For lung ultrasound we rely on the imaging of artifacts to interpret our scans. The main artifact in the lung we see is called reverberation artifact. The physics behind this artifact is briefly explained below.

[figure not shown]
The ultrasound probe is constantly sending ultrasound waves towards whatever tissue is being imaged. When these sound waves get caught between 2 parallel surfaces that are highly reflective, they can bounce around between these highly reflective surfaces and take longer to return to the ultrasound machine.

[figure not shown]
When this happens, you can have an echo that returns to the transducer after a single reflection and this echo will be displayed on the machine in the proper location. Sequential echoes may take longer to return to the

transducer, and due to this increase in time the machine thinks that it is from a surface further away so it will appear deeper on the ultrasound image. So what you end up seeing are bright arcs that occur at equidistant intervals.

Below are examples of normal lung, Bat sign, and A lines.

[figure not shown]
Pleural line and recurrent A lines or reverberation artifact. We see this in normal lung and patients with COPD.

The figure below shows B lines. These are vertical echogenic artifacts that originate from the pleural line, extend to the bottom of the ultrasound screen.

Normal patients have < 3 B lines per rib space

B lines may be seen outside of AHF. Clinical context is crucial! The table below shows other reasons why B lines may be present.

FOCAL	DIFFUSE
Infarct	Pulmonary Edema
Contusion	ARDS
Cancer	Pulmonary Fibrosis
Pneumonia/Pneumonitis	

Beware if you do NOT see A lines! Below are coalesced B lines. So many B-lines blend together, it could look like normal lung but you note no A lines. (This appears better in video). This is, in fact, diffuse B lines.

## 17.2 ULTRASOUND SECURE TRANSFER PROTOCOL

We have previously utilized BOX, an online cloud storage and collaborative environment. Under the strict supervision of Indiana University data stewards, we continue to utilize BOX HEALTH. Such accounts can only be set up via application to the IU data stewards for storage of critical health data. Access to these secure storage sites are then shared with vetted users. Two dedicated BOX HEALTH accounts will be set up for BLUSHED AHF.

All sites currently use Q Path, a vendor based Ultrasound storage system. All sites plus the Core Lab use Q Path in their day to day storage and review of US images. Images are securely transferred via wireless transmission from US machines to Q Path with PHI. All images are stored securely under HIPAA grade security systems. From Q Path, images are then exported to individual computers. During this transfer, PHI is NOT transferred. The only identifying cues left are date/time stamp, which may also be removed. Additional, non-identifiable labels will be added for study purposes. These will then be uploaded into BOX HEALTH.

Two BOX HEALTH folders will be created, one for the investigators and the other for the Core Lab. Prior to uploading to the Core Lab, the images will be de-identified to site by the database manager. Furthermore, the images will be scrambled to avoid interpretation by acquisition order. This further minimizes bias by forbidding site knowledge and order of acquisition. The de-identified images (both by site and PHI) will then be uploaded to the Core Lab BOX HEALTH storage folder for review by the Core Lab.

All interpretations by the Core Lab will be entered into REDCap.

### 17.3 CORE LAB PROCEDURE AND LUNG ULTRASOUND PROTOCOL

#### Introduction

[figure not shown]
The *B-lines Lung Ultrasound Guided ED Management of Acute Heart Failure (BLUSHED-AHF)* – is designed to assess the short-term effectiveness of early LUS guided, protocolized, ED AHF management compared to usual care. ED patients with AHF, who meet all other eligibility criteria, will be randomized within 3 hours of presentation. To achieve this goal, a randomized, controlled, multi-site, strategy-of-care, pilot trial is proposed.

The correlation between B-lines on lung ultrasound and AHF has been well-established. B-lines are an assessment of extra vascular lung water (EVLW). Past studies demonstrate correlation of B-line artifacts with the following: (1) natriuretic peptide levels, (2) invasive hemodynamics, (3) chest xray, (4) clinical assessments, and (5) computed tomography. Moreover, B-lines may resolve after treatment. Lung ultrasound has an additional advantage: it measures patient’s clinical status in real time. Finally, lung ultrasound is easily reproducible and does not carry any radiation exposure risk; thus, it can be repeated at regular intervals without increased risk to the patient.

#### Lung Ultrasound (LUS) Protocol

To best determine the potential value of EVLW measurements using LUS, we will assess patients at multiple timepoints throughout hospitalization. (See Figure 1 – Trial design flow below)

Figure 1: Trial Schematic

For diagnostic purposes, previously published protocols have been the most well-studied.

Each LUS scan consists of 8 sectors as seen in figure 2. (Figure reproduced from Volpicelli et.al.7) Trained research personnel will record and count B-lines in each sector as visualized through one respiratory cycle at each of the time points listed in the Figure. At minimum, each stored video clip will be 6 seconds in length. The total number of B-lines for all 8 sectors will comprise the overall score. With training, the entire scan takes less than 10 minutes.

As patient positioning may impact B-lines, patients will be placed at approximately 45 degrees for all scanning. The CRF will be marked if patients are unable to lie at this angle.

- An 8 zone LUS scan will be done at the following times:
  - T00: initial LUS scan (in ED for screening and eligibility)
  - T02: 2-4 hours after initial treatment (in ED) (+/- 30 minutes)
  - T06: 2-4 hours after T02 or pre-ED discharge, whichever comes first (+/- 60 minutes)
  - HD2: 24 hours after initial scan (Day 2) (+/- 6 hours)
  - HD3: 48 hours after initial scan (Day 3) (+/- 8 hours)
  - HD4: Day 4 (anytime during day)
  - HD5: Day 5 (anytime during day)
  - HD6: Day 6 (anytime during day)
  - HD7: Day 7 (anytime during day)
- **If standard care arm do NOT notify the provider of the results**

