### 4 STUDY DESIGN AND ENDPOINTS

#### 4.1 DESCRIPTION OF THE STUDY DESIGN

A multi-center, prospective, randomized, controlled, unblinded strategy-of-care pilot trial. All potential ED patients will receive an initial LUS scan. Performing LUS is within the standard of care and will be done at no cost to patients. It is not frequently used however, either for diagnosis, prognosis, or to guide clinical therapy. However, treating clinicians will be blinded to these results to minimize contamination of the usual care arm. If clinicians choose to perform their own LUS, those patients will not be excluded. Patients who provide written informed consent and meet all inclusion and no exclusion criteria will be randomized 1:1 to our LUS-guided strategy-of-care vs. usual care. While no further LUS guided intervention will occur for usual care patients, similar to our LUS-guided arm, serial LUS assessments will occur throughout hospitalization as well as pre-specified biomarkers and physical exam. For patients randomized to the strategy-of-care arm, the LUS guided protocol will be initiated and continued until there is a decrease in B-lines to  $\leq 15$  or 6 hours of care has been delivered or patient has left the ED, whichever comes first. Trained research personnel will acquire LUS images. All images will be stored and overread by an independent, expert ultrasonographer blinded to treatment arm.

Safety of patients are paramount. If a potential life threatening etiology is identified, the clinical team will be made aware immediately, irrespective of randomization arm. These occurrences will be recorded in the eCRF. While this will be a rare event, we will a priori establish that an additional patient will be accrued into the study and an additional modified intent to treat population for analysis will be performed, excluding these patients where a life-threatening etiology was identified (i.e. pericardial tamponade).

For patients who do NOT meet eligibility criteria, the results of their LUS will be provided to the clinical team as requested, as these patients are no longer at risk for contamination of the usual care arm.

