#### 4.2.1 PRIMARY ENDPOINT

B-lines  $\leq 15$  at the conclusion of ED AHF management (i.e. patient has left the ED) or maximum of 6 hours after enrollment, whichever comes first.

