### 10.4.3 ANALYSIS OF THE PRIMARY EFFICACY ENDPOINT(S)

The comparison of binary endpoints (B-lines < 15) will be performed using Chi-square or Fishers exact test, as appropriate.

Potential covariates will also be considered in a logistic regression setting to improve precision, which includes baseline co-morbidities, baseline medications (in particular guideline recommended therapies) in-hospital medications, baseline renal function, serum sodium, natriuretic peptide levels, troponin levels, renal function, baseline blood pressure, and discharge medications. Variables such as physical exam, other vital signs, and hemoconcentration may also be included. For NT-proBNP, a percent change greater than 30% and its association with the primary endpoint will be analyzed. This is based on previous work suggesting a 30% change was a key discriminatory threshold for mortality. For hemoconcentration, any increase in value in both hematocrit and hemoglobin during hospitalization will be considered positive. These covariates are known markers of risk and are standard of care assessments for the vast majority of AHF admissions. Covariates with univariately significant association with the outcome will be included together with the treatment indicator in a logistic regression model. Due to limited sample size, we will limit the number of covariates (including treatment indicator) such that there is 10 events per covariate.

---

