#### 10.6.1 ENROLLMENT/ RANDOMIZATION/ MASKING PROCEDURES

Each site will be provided a block randomization table with variable block sizes of 2, 4, and 6. The data coordinating center will continuously monitor the recruitment until the targeted sample size is reached. We will utilize the REDCap Randomization module for web-based randomization.

Due the nature of the intervention and the clinical setting, this is an unblinded trial.

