### **Training**

- Fill out pre-survey
- Watch training video on LUS and scanning protocol (15-20 minutes)
- Review 23 clips together with US director (20 minutes)
- Hands-on scanning (30 minutes)

- Perform 25 clips that have been reviewed by US director and signed off on prior to enrolling a patient (>75% of clips have B lines)
- 20% clips are reviewed by LUS Core Lab ([name])
- Correlation coefficient

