### Image Review

All images will be saved as 6-second video clips. Investigators or study staff will label each clip at the time of scan post-enrollment. For example, Scan 0 is at time of enrollment. Scan 24 is 24 hours post-enrollment, Scan 72 is 72 hours post enrollment. All images will also be date/time stamped, which will be recorded in the local site CRF. Investigators or study staff will fill out a table of their count of B-lines, which will be compared to the Core Lab review. If a rib space is completely whited out with B-lines, this will count as 10 B-lines, half the rib space will count as 5. Importantly, the Core Lab will be blinded to the investigator B-line count.

No PHI will be recorded, only a study ID. Each site will separately and securely store linkages from PHI to the study ID per local IRB approved protocols. Currently, all sites have internal processes to store images for quality control as part of their training programs for fellows and residents. Images will then be transferred to a secure, password protected, access limited server with HIPAA grade security.

Local sites will review images to ensure deidentification. Once de-identified, images will be uploaded to a secure, local server with HIPAA grade security. No post-processing will occur. However, prior to upload to the Core Lab, images will be deliberately mixed with other study patients. This is being done to avoid readers from having 'before and after' images. Images will be then uploaded in batches of 5 patients to a secure, HIPAA grade server.

The Core Lab will then download the images. Importantly, the Core Lab will NOT be a study site to minimize any potential bias or failures of de-identification. Furthermore, the Core Lab will not have access to any clinical information on the patient, further limiting the potential for clinical information to bias image interpretation. To minimize the potential bias of having a single sites images reviewed, images from one site will be mixed with other sites upon arrival at the Core Lab. Reviewers will not see images of patients in chronological order or from only one site at a time.

Formal interpretations will be recorded on a standardized, secure CRF accessible only to the Core Lab and the Data Coordinating Center at IU. All investigators will NOT have access to this data until database lock. Applicable back up and secondary storage will occur on a daily basis

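### The plan does not say which of its two B-line counts, the unmasked site count or the arm-blinded Core Lab count, sets the primary endpoint

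*Combined protocol and SAP*

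**What the plan says.** **Endpoint and analysis.** Section 4.2.1 sets success at 15 or fewer B-lines "at the conclusion of ED AHF management (i.e. patient has left the ED) or maximum of 6 hours after enrollment, whichever comes first". Section 10.4.3 reads: "The comparison of binary endpoints (B-lines < 15) will be performed using Chi-square or Fishers exact test, as appropriate". Section 10.5 sizes the trial on the same outcome. None of them names a reader. (The switch between at most 15 and fewer than 15 is a separate matter.)

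**Site count.** Section 17.3, Lung Ultrasound (LUS) Protocol: "Trained research personnel will record and count B-lines in each sector". Two sentences later: "The total number of B-lines for all 8 sectors will comprise the overall score". Section 17.1, Image acquisition, has staff enter their number on a form or in REDCap after leaving the bedside. Section 10.6.1 states that "this is an unblinded trial". Section 17.3 also tells scanning staff to withhold results from the provider in the standard care arm, so they must know the arm.

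**Core Lab count.** Section 4.1: "All images will be stored and overread by an independent, expert ultrasonographer blinded to treatment arm". Section 17.3, Image Review, adds masking to clinical data and to the site count, and mixes images across patients and sites. On the relation between the two counts it says: "Investigators or study staff will fill out a table of their count of B-lines, which will be compared to the Core Lab review". The second Training part of 17.3 uses the central read for feedback to sites and inter-rater agreement. Image Review also treats the Core Lab reads as formal interpretations, on a CRF open only to the Core Lab and the data coordinating center and closed to investigators until database lock. Section 17.2 enters them in REDCap.

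**Coverage.** Against all images in section 4.1, the first Training list in 17.3 says "20% clips are reviewed by LUS Core Lab".

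**The concern.** At analysis the database will hold two B-line totals per scan, with no rule for choosing between them. Three things make that serious.

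- **The cut-off does double duty in one arm.** Under section 4.1, a count of 15 or fewer in the LUS arm ends guided therapy, and under 4.2.1 the same count at the end of ED care is a success. In usual care the count steers nothing. A reader who knows the arm therefore has a target in one arm only.
- **Counting involves judgement.** Section 17.1 has staff estimate the share of the view that is whited out and adjust the count from there.
- **The two totals may be on different scales.** A sector is capped at 20 lines in section 17.1 and at 10 in section 17.3.

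If the site count is used, reader bias can enter a comparison for which a masked read is already planned. If the choice is left until both sets of data can be seen, the analyst can select between two primary results.

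**Working it through.** **1. Places side by side**

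| Question | Site count | Core Lab count |
|---|---|---|
| Masked to arm? | No (10.6.1; 17.3) | Yes (4.1) |
| Tied to the score definition? | By position: the definition follows the site count (17.3) | Not mentioned there |
| Named in 4.2.1, 10.4.3 or 10.5? | No | No |
| Stated use | Recorded on form or REDCap (17.1); compared with Core Lab (17.3) | Overread (4.1); feedback and agreement (17.3); formal record withheld until lock (17.3) |

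Position favours the site count and data handling favours the Core Lab count. Neither settles the question.

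**2. The plan's own figure.** Inputs from section 10.5: 59 per arm, 25% versus 50%, two-sided 0.05. The pooled proportion is 0.375.

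z = [0.25·√59 − 1.960·√(2·0.375·0.625)] / √(0.25·0.75 + 0.50·0.50) = (1.920 − 1.342)/0.661 = 0.874, and Φ(0.874) = 0.809.

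Exact enumeration of the uncorrected chi-square also gives 0.809. The stated 81% reproduces.

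**3. What differential reading could do.** *Assumption:* the documents give no misreading rate, so a range is shown. Let true success be 25% in both arms, and let d be the share of LUS-arm patients moved from above 15 to 15 or fewer. With X ~ Bin(59, 0.25) for usual care and Y ~ Bin(59, 0.25 + d) for LUS:

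P(significant) = Σ P(X = i)·P(Y = j), summed over all (i, j) where the two-sided test gives p < 0.05.

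| d (points) | Patients, 59·d | Share of true non-responders, d/0.75 | Chi-square | Fisher |
|---|---|---|---|---|
| 0 | 0 | 0 | 5.2% | 2.9% |
| 3 | 1.8 | 4.0% | 6.8% | 4.2% |
| 5 | 3.0 | 6.7% | 9.6% | 6.3% |
| 8 | 4.7 | 10.7% | 16.3% | 11.7% |
| 10 | 5.9 | 13.3% | 22.4% | 16.9% |

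Both tests are shown because section 10.4.3 allows either. Three patients misread in one direction roughly double the false-positive rate under either test.

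**4. The per-sector cap.** Take a scan with two half-whited-out sectors and no other lines. Section 17.1 scores 10 + 10 = 20, not a success. Section 17.3 scores 5 + 5 = 10, a success. One fully whited-out sector plus three lines elsewhere gives 23 or 13. The documents do not assign one cap to one reader. If site staff follow 17.1 and the Core Lab follows 17.3, the same images can fall on either side of 15 with no bias at all.

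**The case against.** A reader might infer that the plan has chosen the unmasked count and confined the Core Lab to comparison. The documents do not support that. The score definition is in the passive, names no reader, is not linked to the endpoint, and would serve equally for a Core Lab total. No sentence limits the Core Lab read to comparison. Scrambled images, a restricted CRF and withholding until lock are what one would expect for outcome data. This stands, and it makes the finding an unspecified source rather than a stated choice. It does not supply the missing rule.

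A reader might also see a contradiction between all images and 20% of clips. The 20% line sits in a training list, just after the clips required before a first enrolment, and most naturally means training clips. It needs a clarifying word.

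Nor do the documents show that reader error would run one way. A premature reading of 15 or fewer in the LUS arm also stops guided therapy, which could reduce true decongestion there. Under the cap of 20, one fully whited-out sector already exceeds 15, so judgement near the cut-off concerns partial white-out and single lines. The false-positive rates are therefore conditional illustrations, not estimates of expected bias.

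**Conclusion.** The concern holds as an unspecified endpoint source. Two counts exist, only one is masked to arm, and no section says which decides the primary result. Read literally, the one score definition points to the unmasked count; the handling of the Core Lab reads points the other way.

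The possible size runs from 5.2% with no shading to 22.4% at 10 points (chi-square), or 2.9% to 16.9% (Fisher). It rests on three assumptions: the site count is used, shading occurs only in the LUS arm and only towards success, and true success is 25% in both arms. The cap discrepancy needs none of these to matter.

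This should be settled before anyone sees outcome data by arm, because the primary result depends on it and the masked read is already planned.

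**What to change.** - In 4.2.1 and 10.4.3, state that the primary endpoint and all other B-line efficacy endpoints use the arm-blinded Core Lab 8-sector count of all trial scans.
- In 17.3, limit the site count to eligibility, real-time guidance and a sensitivity analysis of the primary comparison.
- Give a rule, fixed before lock, for missing or unreadable Core Lab reads.
- Reconcile the per-sector cap between 17.1 and 17.3, and apply one cap to both readers.
- Say that the 20% review refers to training clips.

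The cost is wording. Section 4.1 already plans the overread of all images, and 59 per arm, 81% power and 130 patients are unchanged. Two limits remain. Some patients eligible by the site count will be at or below 15 at baseline by the Core Lab; this adds noise to both arms alike, and their number should be reported by arm. A masked read also does not remove acquisition bias, because the unmasked operator picks the window with the most lines (17.1, Image acquisition).

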### **Data Collection Form**

- B lines
- Pleural effusion size and location
- Who is performing the scan
- Document time to perform scan
  - Begin with time stamp of first image and end with time stamp of last image +6s

### **Training**

- Fill out pre-survey
- Watch training video on LUS and scanning protocol (15-20 minutes)
- Review 23 clips together with US director (20 minutes)
- Hands-on scanning (30 minutes)

- Perform 25 clips that have been reviewed by US director and signed off on prior to enrolling a patient (>75% of clips have B lines)
- 20% clips are reviewed by LUS Core Lab ([name])
- Correlation coefficient

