### 10.4.4 ANALYSIS OF THE EXPLORATORY ENDPOINT(S)

*DAOOH*: Will be compared using T test or Wilcoxon rank-sum test, as appropriate.

If the distribution of 30 or 90 days *DAOOH* is skewed, the T test may not perform satisfactorily. An alternative approach to evaluate the robustness of the analysis, is to treat *DAOOH* as an ordinal outcome and use the proportional odds (PO) regression model to compare the two arms. The PO model is a generalization of the Wilcoxon (Mann-Whitney) test to estimate the shift in the underlying distribution of *DAOOH* by the intervention. The PO regression allows for adjustment of baseline covariates to enhance power.

We will examine the distribution of B-lines measurements for the groups with and without events separately. Both absolute number and relative change will be evaluated. Receiver Operating Characteristic (ROC) curves will be plotted together with area under the curve (AUC) calculated to understand the prediction performance of the B-line measurements. Sensitivity, specificity, positive and negative predictive values will be computed at a number of thresholds of B-line measurements to understand the trade-off between false positive and false negative. Confidence intervals of statistical measures will be constructed using the bootstrap method. Although 15 B-lines have been previously identified as a valid threshold, an alternative number may be more useful in the ED setting.

For reproducibility analysis, generalized linear mixed-effects models will be fitted to estimate the inter- and intra-observer variability, where both patients and observers are treated as random effects.

We will compare parameters used to identify congestion. This will include a comparison between B-lines measurements and other markers, such as physical exam, NTproBNP, eGFR, and hemoglobin/hematocrit. Bootstrap method will be used for the comparison to account for correlations between the markers and the B-line measurements. We will consider two strategies to explore potential multivariate models:

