## **Training**

All physicians and research staff will undergo in-person training sessions led by the US PI at each site using a standard protocol. Both didactics and proctored bedside scans will occur. This will ensure technique and equipment settings are standardized. Published literature provides strong evidence that LUS can be learned with minimal training: as little as 30 minutes yields excellent correlation with expert sonographers. In addition, established protocols will be utilized for transfer and storage of images.

To ensure ongoing quality assurance, feedback will be provided to each site for every 10 patients, or more frequently as needed if initial review suggests inconsistency. An independent, blinded, expert ultrasonographer will review the images. Concordance with clinical site interpretations will be provided. Additional training will be provided by the

Figure 3: Counting of B-lines using Lung Ultrasound

central reviewer as needed. Inter-rater agreement on B-line counts will be reported at the end of the study.

The CORE lab is led by [name] MD: she is an internationally recognized expert in LUS. She has a proven record of training, both for research and clinical purposes. She has substantial experience in the collation, interpretation, and reporting of LUS images.

**Counting of B-lines:** (Figures courtesy of [name] MD)

B lines will be counted as the number seen per acoustic window. See Figure 3.

In the situation where there is 'white out' or diffuse B lines in a rib space, this will be counted as 10 B-

lines. Half the rib space will be 5. 10 will be the maximum number of B lines per sector.

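### The one statistic named for checking site B-line readers against the Core Lab is a correlation coefficient, which does not detect systematic over- or under-counting around the cut-off of 15

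*Combined protocol and SAP*

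**What the plan says.** **Checks on readers**

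- Section 17.3, first Training list. Before enrolling, a reader must "Perform 25 clips that have been reviewed by US director and signed off on prior to enrolling a patient". The list then says "20% clips are reviewed by LUS Core Lab" and ends with "Correlation coefficient". It gives no type of coefficient, acceptance limit or consequence.
- Section 17.3, second Training section. An independent blinded expert reviews the images, and "feedback will be provided to each site for every 10 patients, or more frequently as needed if initial review suggests inconsistency". "Concordance with clinical site interpretations will be provided", with further training by the central reviewer as needed. "Inter-rater agreement on B-line counts will be reported at the end of the study". No index is named for the concordance or for the agreement.
- Section 17.3, Image Review. Site counts are compared with the Core Lab review; the method is not stated.
- Section 4.1. "All images will be stored and overread by an independent, expert ultrasonographer blinded to treatment arm".
- Section 10.4.4. Mixed-effects models are fitted "to estimate the inter- and intra-observer variability, where both patients and observers are treated as random effects".

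**What the counts decide.** Entry requires more than 15 lines (5.1). LUS-guided care continues until the count is 15 or fewer, subject to time and location limits (4.1). In the LUS arm, further therapy follows LUS only (6.1.1).

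**How a white-out is scored.** Section 17.1 (Counting B Lines) gives 20 for a full and 10 for a half white-out, with a sector maximum of 20. Section 17.3 (second Training section and Image Review) gives 10 and 5; the second Training section sets the maximum at 10.

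No section specifies mean bias, limits of agreement, agreement at 15, or a limit at which a reader is retrained.

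**The concern.** Correlation measures whether two readers rank and space the scans alike. It does not measure whether they arrive at the same number. This trial acts on the number: a reader who consistently undercounts can screen out eligible patients and end LUS-guided escalation early, and one who overcounts does the reverse. These decisions are made at the bedside from site counts, so a later overread cannot undo them. Different habits at different sites would also add variation between sites in how the LUS strategy is delivered. A systematic error is plausible because the two scoring passages differ by a factor of two on whited-out zones.

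**Working it through.** The plan states no reader-agreement figure or pass mark, so there is nothing of its own to reproduce. The check has three steps.

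**1. Correlation under systematic error.** Let X be the Core Lab total and Y = a + bX the site total, with b > 0. Then r = b·Var(X) / [SD(X) · b·SD(X)] = 1 for any a and b. Rank correlation is likewise 1.

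**2. The documents' own scoring conflict.** Take one fully whited-out zone with the other seven clear. The total is 20 under 17.1 and 10 under 17.3. With one line in each of three further zones (four zones involved, as 5.1 requires), the totals are 20 + 3 = 23 and 10 + 3 = 13. Both examples fall on opposite sides of 15.

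**3. Share of scans changing side.** With F the distribution function of X, the share is |F(15/b) − F(15)| for a proportional error and |F(15 − a) − F(15)| for a shift. In whole lines, the totals that change side are:

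- +20%: 13 to 15 (1.2 × 13 = 15.6, read as 16)
- +30%: 12 to 15 (1.3 × 12 = 15.6, read as 16)
- −30%: 16 to 22 (0.7 × 22 = 15.4, read as 15)
- +5 lines: 11 to 15
- −5 lines: 16 to 20

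The documents give no distribution for the 8-zone total, so two assumed sets were simulated, with 400,000 scans for each distribution:

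- *Endpoint-calibrated set:* gamma totals with the share at 15 or fewer fixed at 25%, 37.5% or 50%. The outer values are the rates in 10.5, and 37.5% is their mean. The coefficient of variation was assumed to be 0.6 to 1.0.
- *Pilot set:* negative binomial totals with the means and SDs in 2.2 (78/47, 44/33, 26/26, 48/48, 20/23). The first pilot used 28 sectors, so applying these to 8 zones is an assumption.

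No random reading error was added. In the calibrated set r stayed at 0.998 or above, and the share changing side of 15 was:

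| Reader error | Share changing side of 15 |
|---|---|
| +20% | 4% to 13% |
| +30% | 6% to 17% |
| −30% | 9% to 24% |
| +5 lines | 7% to 22% |
| −5 lines | 7% to 18% |
| Factor of two | 12% to 41% |

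In the pilot set, errors of 20% to 30% or 3 to 5 lines gave 1% to 13%, and a factor of two gave 2.5% to 24%. A separate clip-level run, also on assumed distributions, took a reader at 0.7 times the Core Lab count or a 10-versus-20 white-out mismatch. It gave clip-level r of about 0.97 to 0.99 with roughly 6% to 15% of scans changing side.

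**Would an absolute-agreement coefficient suffice?** In the calibrated set the concordance correlation falls to 0.80–0.89 for −30% and 0.51–0.67 for halving. It stays at 0.90–0.996 for +5 lines, where 7% to 22% of scans change side. A single coefficient is therefore not enough.

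**The case against.** The strongest reply is that the correlation is one bullet in a training outline, not the whole safeguard. The US director signs off 25 clips before a reader enrols. A blinded expert reviews images during the study, sites receive concordance feedback every 10 patients, and retraining follows as needed. The observer effect in 10.4.4 can show differences between readers. The type of coefficient is also unstated; an absolute-agreement intraclass coefficient would respond to bias, at least to large proportional errors.

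Most of this stands. A reader might infer that nothing intervenes before the end-of-study model; the second Training section shows otherwise. A reader might also infer that a biased reader would pass or be certified on a high r. The documents do not support that, because the correlation has no pass mark and sign-off is a separate step.

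The unit is a further fair point. The first Training list concerns clips, while the cut-off applies to the 8-zone sum, so a clip-level r does not translate directly into misclassified scans. Sector caps also prevent a uniform doubling in heavily affected zones.

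What the reply does not supply is a measure. The sign-off, the concordance and the count comparison have no stated index or limit. The mixed model reports at the end and does not address agreement at 15. The feedback is the right vehicle, but its content is unspecified.

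**Conclusion.** The point holds as a cheap improvement. The only agreement statistic explicitly named for the Core Lab check of site readers is an unspecified correlation. In its ordinary form it does not respond to the error that matters at a fixed cut-off, and with no limit attached it would flag no one.

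The size depends on assumptions: roughly 1% to 24% of scans changing side of 15 for errors of 20% to 30% or 3 to 5 lines, with r near 1. It is tempting to quote one scan in seven. That is a single scenario, for example +30% with 37.5% of scans at 15 or fewer and a coefficient of variation of 0.6 (14.6%). The documents give neither the 8-zone distribution nor the size of any reader error.

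A reader might go on to infer a loss of power for the primary comparison. The documents do not settle this: 4.2.1 does not say whether site or Core Lab counts define the endpoint, and 4.1 has all images overread blind to arm. The secure consequence concerns eligibility and LUS-guided treatment.

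**What to change.** 1. In the first Training list of 17.3, replace the correlation coefficient with the mean difference from the Core Lab per clip, with limits of agreement.
2. In the feedback every 10 patients (second Training section of 17.3), report the mean difference with limits of agreement on the 8-zone total. Add percent agreement or kappa for 15 or fewer versus above 15. State in advance the limit that triggers retraining.
3. Reconcile the white-out and sector-maximum passages in 17.1 and 17.3, so that site readers and the Core Lab score alike.
4. Say how this feedback fits with Image Review, which withholds Core Lab interpretations from investigators until database lock, and reconcile the 20% review of clips with the overread of all images in 4.1.

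The cost is slightly more analysis work, using the overreads already planned. Agreement at the cut-off needs complete 8-zone scans rather than isolated clips: 25 sign-off clips amount to only about three scans (25/8 = 3.1). That measure therefore belongs in the ongoing feedback rather than in the training check.
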